## Objectives

**Primary Objective 1 (intervention):** To determine whether behavioral therapy coupled with anodal tDCS will improve the language performance of participants with PPA and MCI more efficiently and for greater duration than behavioral therapy alone (i.e. in the sham condition). tDCS targets will be the supramarginal gyrus (SMG), middle temporal gyrus (MTG) and inferior frontal gyrus (IFG). These areas are critical for both phoneme-grapheme conversion and for access to orthographic representation of words and their meaning in the spelling process (Cloutman et al., 2009). For individuals with naming or working memory/repetition deficits, tDCS targets will also be IFG, MTG, angular gyrus (AG), and SMG, as these are also areas of the brain consistently activated in these tasks (Jarso et al., 2013; Philipose et al., 2007). For individuals with executive functioning deficits, the tDCS target will be the dorsolateral prefrontal cortex (DLPFC) to compare language vs. executive functions after stimulation of the DLPFC. For individuals receiving home-based tDCS and computerized cognitive therapy, tDCS targets will include perisylvian areas and their right hemisphere homologs. For individuals receiving home-based tDCS there will be an optional 3-week cognitive behavioral therapy (CBT) where the tDCS target will be the LDLPFC.

Hypothesis 1a: Both behavioral therapy and combined tDCS-behavioral therapy will result in improved language performance for trained and untrained stimuli, from baseline to post-treatment; however, goals will be achieved more rapidly with the combined intervention.

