Hypothesis 1b: Improvements in language achieved with combined tDCS-behavioral therapy but not behavioral therapy alone will persist at 2 weeks, 2 months and 6 months post-intervention. Hypothesis 1c: Stimulation of the propose areas during behavioral therapy will improve performance in other language and cognitive functions specific to the region of interest. Specifically, for SMG, improvements will be observed in spelling, naming, working memory and repetition; and for IFG and MTG, in spelling, naming, working memory, articulation, and syntactic comprehension. Hypothesis 1d: The therapeutic effect of tDCS will exhibit an interaction between hemisphere of stimulation (left vs. right) and stage of disease (early vs. middle), such that left hemisphere stimulation will be more effective at an early stage, whereas at later stages right hemisphere stimulation. Hypothesis 1e. Improvements in language achieved with combined IFG tDCS-behavioral therapy or sham and behavioral therapy alone will correlate with increases in daily physical activity and evening sleep efficiency and quality (using both self-report and objective measures) and there will be greater improvements in sleep efficiency and exercise in the tDCS condition as opposed to sham, because the area we target (left or right IFG) with 2x2 in electrodes incorporates premotor and motor areas that have

been found to improve the perceived difficulty and amount of exercise and sleep efficiency.

Hypothesis 1f: Beginning with a 3-week CBT treatment with tDCS over the DLPFC before beginning computerized cognitive/speech therapy at home will foster motivation and engagement in the consequent therapy by establishing routine, form, and helping manage psychological barriers to therapy beforehand.

**Primary Objective 2 (imaging):** To develop biomarkers for the effects of intervention using H-MRS. We will use H-MRS to detect NAA and GABA before, after and at follow-up intervals and evaluate the correlation between: (1) NAA/ GABA levels and (2) spelling, naming, and/or repetition accuracy of participants with PPA and MCI at each time point.

Hypothesis 2a: We hypothesize that tDCS coupled with behavioral therapy will result in enhanced, relative to behavioral therapy alone (with sham tDCS), levels of NAA at the stimulation sites where tDCS resulted in improved spelling relative to behavioral therapy alone.

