## Primary Objective 3 (molecular mechanisms)

**Part 1:** (A) To determine whether BDNF levels in plasma or saliva are related to language and cognitive decline in PPA, differently in men and women (cross-sectionally, before treatment). (B) To evaluate whether tDCS modulates BDNF levels and language and cognitive performance differently in men and women, relative to baseline (before treatment). We will measure BDNF levels, as well as other synaptic proteins (e.g., NPTX2, NRXN2a, AMPA4), language and cognitive performance, before, immediately after and 6 months post-treatment.

**Part 2:** To measure the correlation between tDCS-induced changes in functional connectivity and BDNF in men and women. We will measure brain and skull anatomical variables from scans, and analyze data from resting state functional magnetic resonance imaging (rsfMRI) before, immediately after, and 6 months post treatment.

*Hypotheses*: (A) tDCS will induce differential functional connectivity (FC) changes in men and women; (B) these FC changes will correlate with changes in BDNF blood levels; (C) and BDNF changes will correlate with changes in therapy outcomes in men and women, after controlling for potential sex-dependent cranial and neuroanatomical differences. (D) Changes will last for up to 6 months.

**Part 3**: To identify whether gene mutations (e.g., val66met) that affect BDNF secretion in men and women with PPA predict tDCS effects on BDNF levels, behavioral outcomes and FC network modulations. We will analyze behavioral tDCS effects (over sham) with regard to the interaction between genetic mutation and sex. We will also test whether known mutations that are responsible for Alzheimer's disease pathology e.g., the APOE4 affect tDCS effects, since this genetic mutation can be isolated with the same genetic sequence procedure (Taqman). We will carry out genetic testing at the beginning of treatment and stratify tDCS groups accordingly.

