conditioning using tDCS have received Johns Hopkins IRB approval. We will use either the same equipment as [name] and his team have used (a Chattanooga lonto Device) as well as the same application technique, recently acquired state-of-the-art device using special software for doubleblinding (Soterix 1x1 CT: clinical trials), or a Neuroelectrics Starstim 8 device, which is a high-definition tDCS cap with higher precision. In order to administer intervention during the global pandemic and in a virtual manner, we will offer the option of remote stimulation (Soterix mini-CT device and MIND STIM+, YBrain). Attached please find letters from Clinical Engineering documenting that the tDCS devices have undergone clinical inspection as well as the manuals. When remote devices are implemented, participants and spouses will be trained prior to intervention and sessions will be conducted in real-time via video conference (e.g., Zoom). Stimulation will be delivered at an intensity of 1-2mA (estimated current density 0.04 mA/cm2; estimated total charge 0.048C/cm2) for a maximum of 20 minutes in the tDCS groups and for a maximum of 30 seconds in the Sham group. For both interventions (tDCS and Sham) the electrical current will be increased in a ramp-like fashion at the onset of the stimulation eliciting a transient tingling sensation on the scalp that usually disappears over seconds. Although the ramping process requires the researcher's input, it is now feasible to blind study staff who will be applying tDCS, as well as participants, as we now have a box that allows another member of the team to set the box to "tDCS" or "sham" without the knowledge of the researcher providing the therapy. In the Starstim 8 and remote devices, double-blinding is achieved through codes known only to the PI who is not administering any stimulation or evaluation, so both the technician or professional who administers the stimulation and evaluation are blind to the current condition being either actual tDCS or sham. After the ramping, in the sham condition, the intensity drops to 0 mA. These procedures have been shown to successfully blind participants as to whether they were members of experimental or control groups (Gandiga et al., 2006). The sites of tDCS application will be determined by the type of therapy used and the PPA variant group or MCI and will be either the inferior frontal gyrus (IFG), the supramarginal gyrus (SMG), or the middle temporal gyrus (MTG) or a combination as shown in the literature. A recent meta-analysis of the functional neuroimaging literature on spelling has not yet identified clearly the neural substrates for PG conversion; the most plausible network includes the inferior parietal lobule including the supramarginal gyrus (Purcell et al., 2011). This area has also been identified as a critical area for spelling in the lesion literature as well. Another plausible area that shows activations during both PG conversion and lexical (word) spelling is the inferior frontal gyrus (IFG) (Purcell et al., 2011) and lesions in the IFG are associated with impaired PG conversion (Beeson et al., 2010). The stimulation site of IFG will be determined between F7 and F8 electrodes and that of SMG between TP3 and TP4 using the EEG 10-20 electrode position system (Homan, 1988). Additionally, studies have reported positive results of tDCS over the left dorsolateral prefrontal cortex (DLPFC) leading to improvement in attention deficits due to stroke, Parkinson's disease, and major depression (Boggio et al., 2006, 2007; Fregni et al., 2006; Kang et al., 2009). In addition to improving attention, anodal tDCS at the left DLPFC has been shown to improve working memory in TBI patients (Ulam et al., 2015). We hypothesize that anodal tDCS over the L DLPFC when administered in combination with cognitive training will improve language performance of PPA and MCI participants more than behavioral therapy alone, and that improvements may generalize to some other cognitive functions. The dependent variable will be the same baseline and post-therapy evaluation as described above that will take place before, after, 2 weeks and 2 months post-stimulation for each stimulation condition (see Table 1). These same areas, predominantly on the left, are activated during naming (Jarso et al., 2013) and working memory (Philipose et al., 2007). In most cases of PPA and all cases of MCI, we will stimulate areas of the left hemisphere that are not atrophied. In the most advanced cases of PPA, with severe left hemisphere atrophy, we will stimulate the same sites in the right hemisphere in order to stimulate its compensatory mechanisms (see Hypothesis 1d). By this design we will be able to achieve a within-subject design for all conditions as well as to evaluate immediate, short- and long-term effects of each stimulation site without confounds and without any carry-over effects. We will also conduct a 6-month language evaluation to assess the overall therapy gains.

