## b. Study duration and number of study visits required of research participants.

Before any intervention participants will be enrolled in a control condition for 12 weeks during which no therapy will be provided to enable us to assess their personal decline rate. After this period they will be randomly assigned to either sham or tDCS experimental conditions. Three pre-training sessions may be proposed to test the tDCS experimental conditions before training. After 1-3 weeks of tDCS application (3-5 sessions in a week, 5-15 sessions per stimulation site) there will be an interval of approximately 2 months and then we will implement the other two tDCS conditions in a within-subject cross-over design, an example of which is shown in Table1. We will follow-up the participants with 2-week, 2-month and a final 6-month follow-up sessions. For those participants who are long-distance, at the 2-week time point we may use a video conferencing tool such as GoToMeeting to administer the assessments. This is to mitigate the costs of travel for a short appointment. In these sessions we will administer the behavioral therapy assessment as described in the therapy section. We will test participants with both the practiced items and unpracticed items to look at generalization effects to untrained items. Given that we will test each participant in different conditions, an example of the sequence of conditions is shown in Table 1. After the final evaluation of interventions, we will offer an optional remote extension phase. This will consist of 18 additional months of intervention: 50 therapy sessions+tDCS (in 10 weeks) every 3 approximately months for a 18-month period, depending on availability, using different areas of stimulation (either the IFG, SMG, MTG, or DLPFC or Precuneus based on previous literature, see above in tDCS methods for details) for up to 18 months in total. We will complete another full evaluation of language and cognitive skills at the end of the stimulation phase. We will compare maintenance of therapy gains for individuals who participate in these remote sessions to those who do not, to answer the question whether tDCS effects may be extended beyond the initial 2-month period follow-up, up to 18 months and whether the rate of decline may change. This is very important because long periods of interventions and followup are needed in studying intervention outcomes in a neurodegenerative disorder.

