## c. Statistical plan including sample size justification and interim data analysis.

Design. This is a crossover trial, where each participant will be randomly assigned to receive either "IFG tDCS, then sham then SMG (in case a second stimulation site is implemented)" (group1) or "SMG then sham then IFG" or "sham then IFG then SMG". In case a second stimulation site is not implemented participants will receive either sham and then tDCS (group 1) or tDCS and then sham (group 2). Based on previous studies regarding long-term effects of tDCS (see Fiori et al., 2011; Fridriksson et al., 2011; both looking at 3-weeks post-stimulation in participants with aphasia) and given the degenerative nature of PPA (and some cases of MCI), we assume that even though the effect of tDCS on the absolute level of the outcome may or may not persist at 2 weeks, the effect on the rate of decline persists no longer than 2 weeks. Analyses. The primary analyses will be a robust type of repeated measures Multivariate ANCOVA. Specifically, for each subject (i) and at follow-up times t=immediately after treatment, then 2 weeks and 2 months, we will consider the data  $IFG_{ti}$ ,  $SMG_{ti}$ , and  $S_{ti}$ ; here,  $IFG_{ti}$  is the change of outcome from just before IFG tDCS treatment to time t after IFG tDCS treatment for subject i; and similarly for SMGt,i, and St,i for IFG tDCS and sham. For the behavioral methods, change of outcome is considered the difference (before and after therapy) of the independent measure of initial letter-sound associations learned. Then the research hypothesis that IFG (or SMG) treatment is superior to sham will be tested by testing the hypotheses that the distribution  $pr(R_{ij} - S_{t,i})$  (or  $pr(L_{t,i} - S_{t,i})$ ) is not centered at zero. This will be done nonparametrically by obtaining the latter null distributions by the random permutation of the treatment labels (IFG, S, SMG) of the data for each patient (Rosenbaum, 1988). The design effect, i.e., the ratio of sample sizes needed by an independence design vs. the crossover design to achieve a given power, depends on the correlations of outcomes across times and treatments. We have calculated that this crossover design with 30 participants and design effect of 1.5 has power 75% to detect an effect size of 0.8 between a tDCS site and sham treatment. In secondary analysis, we will use regression to examine if any effects of tDCS vary across participants with different characteristics such as age and atrophy volume. The present design allows us to evaluate the language and neuromodulatory effects of both IFG and SMG stimulation as well as language therapy alone (in the condition of sham stimulation).

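### Hypothesis 1d predicts a hemisphere-by-stage interaction, but side of stimulation is set by severity and left atrophy and never randomised, so the design cannot test it free of confounding

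*Combined protocol and SAP*

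**What the plan says.** Under Primary Objective 1, Hypothesis 1d says the tDCS effect will show an "interaction between hemisphere of stimulation (left vs. right) and stage of disease (early vs. middle"), with left stimulation more effective early and right stimulation later.

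Section 3a (tDCS methods) then allocates side by clinical state. On the left: "In most cases of PPA and all cases of MCI, we will stimulate areas of the left hemisphere that are not atrophied". On the right: "In the most advanced cases of PPA, with severe left hemisphere atrophy, we will stimulate the same sites in the right hemisphere". The second sentence cites Hypothesis 1d as its reason, and the next sentence says the design evaluates each stimulation site free of confounding.

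Randomisation is described in two places. Section 3b, after the 12-week control period: "After this period they will be randomly assigned to either sham or tDCS experimental conditions". Section 6c, where one site is used: "participants will receive either sham and then tDCS (group 1) or tDCS and then sham (group 2"); where two are used, it is the order of IFG, SMG and sham. Table 1 lists left-sided active sites only. The one stratification statement is in Primary Objective 3, Part 3: "We will carry out genetic testing at the beginning of treatment and stratify tDCS groups accordingly".

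Right-sided stimulation is mentioned in three other places. Under Primary Objective 1: "For individuals receiving home-based tDCS and computerized cognitive therapy, tDCS targets will include perisylvian areas and their right hemisphere homologs". Section 6a repeats this for home-based participants and names pre-to-post language scores as their outcome. Hypothesis 1e refers in passing to IFG on either side. None of the three says how side is chosen.

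The nearest planned analysis is the secondary one in section 6c: "regression to examine if any effects of tDCS vary across participants with different characteristics such as age and atrophy volume". It names neither hemisphere nor stage.

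**The concern.** An interaction between side and stage is a contrast of four groups: early-left, early-right, middle-left and middle-right. Testing it needs data that identify all four, and a reason to believe that those stimulated on the left and on the right at a given stage are otherwise comparable. The section 3a rule works against both. It sends later-stage participants with severe left atrophy to the right and nearly everyone else to the left, so the allocation itself builds in the pattern that 1d predicts.

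The risk is a report that right stimulation suits later disease when the data show only that people with more left atrophy respond differently from people with less. Such a statement could influence the choice of side in later work.

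**Working it through.** **The plan's own power figure.** Section 6c gives 75% power for 30 participants, design effect 1.5 and effect size 0.8. Then 30 × 1.5 = 45 equivalent independent participants, or 22.5 per arm. SE = √(2/22.5) = 0.298; 0.8/0.298 = 2.68; power = Φ(2.68 − 1.96) = 76.5%, or 74.6% with the noncentral t (two-sided 5% assumed; the plan states no alpha). The figure reproduces. It concerns a tDCS site against sham and says nothing about 1d.

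**Estimability under the section 3a rule.** Let the outcome be each person's tDCS-minus-sham difference. The model for 1d has four columns: intercept, stage (early 0, middle 1), hemisphere (left 0, right 1) and their product. With cell means μ, the interaction is

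(μ_MR − μ_ML) − (μ_ER − μ_EL).

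Assumption: the most advanced cases of section 3a correspond to the middle level of 1d. This is the natural reading, but no stage term is defined. On it, early-right is empty.

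| Cells filled | Rank | Interaction |
|---|---|---|
| early-left, middle-right | 2 of 4 | not estimable |
| early-left, middle-left, middle-right | 3 of 4 | not estimable |
| all four | 4 of 4 | estimable |

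In the first row the only available contrast is μ_MR − μ_EL, which is the sum of the stage effect, the hemisphere effect and the interaction: one equation in three unknowns. In the second row μ_MR − μ_ML is available, but μ_ER is not.

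**Can home-based participants fill the gap?** Add one column for setting, with an additive shift δ for home. There are now five unknowns.

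- Clinic early-left, middle-left and middle-right filled, plus home early-right only: four cell means, rank 4 of 5, not estimable.
- The same, plus one further home cell: δ comes from the cell seen in both settings, μ_ER follows, rank 5 of 5, estimable.
- Clinic middle-left empty, plus home early-right and one further home cell: four cell means for five unknowns, rank 4 of 5, not estimable. Home middle-left and a third home cell would be needed as well.

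This route also needs home participants to have a sham contrast. Section 3a describes blinded sham on remote devices, so the contrast may exist, but section 6a names only pre-to-post scores for this group. If the Primary Objective 1 sentence means both hemispheres in one person, the route may give no left-right comparison at all.

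**Confounding.** Whatever the rank, the expected right-minus-left difference at a given stage is the side effect plus the difference in response due to left atrophy and severity. Randomising side, or crossing it over within a person, would remove the second term on average. Sections 3b and 6c and Table 1 do neither. The crossover protects tDCS minus sham within a person; left against right remains a comparison between people. Adjusting for atrophy volume relies on the two sides sharing a range of atrophy, which a rule based on severe left atrophy would leave small or absent.

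**The case against.** The side rule is a clinical decision, and 1d is one of six sub-hypotheses (1a to 1f) with no stated model. A misleading claim about side would therefore have to come from an analysis that the plan does not describe. Both points stand, and they limit the weight of the matter. Nothing here questions who receives which side, only the inference drawn from it.

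Three stronger readings are tempting, and the documents support none of them.

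- *The interaction can never be estimated.* The text does not go that far. Home-based participants, or the mention of IFG on either side in Hypothesis 1e, could supply early-right data. The flat statement holds only for the section 3a rule taken alone and on the stage mapping above.
- *The trial's main comparison is compromised.* It is not. Each participant serves as their own control for tDCS against sham, and that contrast does not depend on how side was chosen.
- *The right-stimulated group must be empty, because section 4 excludes advanced stages.* Section 3a may mean the most advanced among eligible participants. The two passages need reconciling, but an empty group does not follow.

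One might also want a confidence-interval width for the right-stimulated group. The documents give no cell counts, so any such figure would rest on invented numbers. That group may be small.

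**Conclusion.** The plan presents 1d as a hypothesis to be tested, and the stated design cannot test it free of confounding. Under the section 3a rule alone, with the most advanced cases taken as the middle level of 1d, the rank is 2 or 3 of 4 and the interaction is not estimable. With home-based data it may become estimable, on conditions that the plan does not establish. In every case side is not randomised, so a left-right or interaction estimate is confounded with severity and left atrophy, and the section 3a statement that sites are evaluated free of confounding does not hold for hemisphere. The conclusion about confounding needs no assumed numbers; the one about estimability rests on the stage mapping. The effect is confined to 1d. The plan should be changed, but the primary analysis does not depend on it.

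**What to change.** 1. Restate 1d as descriptive.
2. Define early and middle stage by a baseline measure, and tabulate the number of participants in each hemisphere-by-stage cell.
3. Report tDCS minus sham with confidence intervals separately in left-stimulated and right-stimulated participants, and report home-based participants separately.
4. State that side was not randomised and was set by severity and left atrophy, so a difference by hemisphere, or by hemisphere and stage, cannot be attributed to side; and that under the section 3a rule alone the interaction is not estimable.
5. Limit the section 3a statement about freedom from confounding accordingly.
6. Reconcile the section 3a reference to the most advanced cases with the section 4 exclusion of advanced stages. Which should stand is not a matter for this review.

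The cost is wording, one stage definition and one table. Treatment, sample size and visits do not change. The sponsor gives up the claim to test the 1d interaction. The within-person estimates by side remain, though the right-sided one may be too imprecise to support a conclusion.
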